Fractional CO2 LASER vaginal therapy has recently been studied for the treatment of GSM. LASER therapy is currently commercially available and has FDA clearance for use in gynecology. Current evidence shows that with treatment, histologic changes of the vaginal epithelium have shown regeneration to a premenopausal state, along with subjective improvement in GSM symptoms and sexual function. Using LASER therapy, Zerbinati et al described response by the vaginal epithelium with thickening, superficial shedding and renewing of stratified epithelium, which was maintained 2 months after treatment.[4] Athanasiou et al also described the impact of LASER therapy on the vaginal flora, decreasing the vaginal pH to 4.7 (p<0.001) and increasing the Lactobacillus colonies from 30% to 79%.[5] Based on the impact this promising new regenerative therapy has on the vaginal epithelium and microbiome, we anticipate this may have a positive impact on women with rUTI.

- We therefore hypothesize that fractional CO2 LASER vaginal therapy is non-inferior to topical vaginal estrogen therapy for the treatment of rUTI.
  a. Primary Outcome: Improvement in recurrence of culture positive UTI
- 2. We also hypothesize that LASER therapy will improve the urinary and vaginal microbiome, decreasing the uropathogenic presence and increasing Lactobacillus.
  - a. Measurement 1: The number of UTI with UPEC isolated from patients
  - b. Measurement 2: The pH of the vagina as a proxy for presence of Lactobacillus sp.
  - c. Measurement 3: Categorize vaginal and urinary microbial communities

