# Methods

We propose a randomized controlled trial to evaluate the clinical difference between the LASER and topical vaginal estrogen in treating patients with rUTI. We expect to enroll 94 patients, to power this study to 80% with type I error of 5%, expecting a recurrence in UTI of 16% and non-inferior margin of 20%. This is accounting for a 10% drop out rate. While this clinical margin is wide, this project will provide us with ample data to apply for external funding, along with a wealth of microbiome data to evaluate in Aim 2. Menopausal women with rUTI will be recruited from the Departments of Urology and Gynecology. If they meet inclusion criteria, they will be randomized to treatment of topical vaginal estrogen or LASER therapy. LASER therapy will be applied 6 weeks apart for a total of 3 treatments. Topical vaginal estrogen will be prescribed per the patient's formulary and preference. Patients will be monitored for recurrence of culture positive UTI.

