# Vaginal Estrogen Protocol

Women randomized to vaginal estrogen therapy will be offered vaginal cream. Two FDA approved formulations exist and patients will be offered the choice between the two, which may also be dependent on their insurance formulary preference.

- 1. Conjugated estrogen (Premarin): 0.5 gm per vagina twice weekly
- 2. Estradiol (Estrace): 1gm per vaginal twice weekly

**Specific Aim 1:** Evaluate the number of culture positive, symptomatic UTI in women following randomization to vaginal estrogen and vaginal LASER therapy.

Methods: Following randomization and treatment initiation, patients will be monitored for recurrence of UTI. Patients will be encouraged to call the treating physician for treatment antibiotics according clinical judgment. Standard urine cultures will be obtained along with information about what type of antibiotic treatment was administered. Validated questionnaires will also be collected to monitor symptoms of GSM and also of urinary incontinence symptoms (Appendix A and B). Patients will be followed for 6 months with evaluations at baseline, 4 months, and 6 months.

**Specific Aim 2:** Characterize the urinary and vaginal microbiome at baseline and at 4 months of patients in each group.

Methods: Baseline vaginal and catheterized urine samples will be collected along with samples at 4 months. Standard catheterized urine cultures will be performed and if symptomatic, treated appropriately (per Aim 1). Microbiome of urine and vaginal environments will then be analyzed using 16S ribosomal DNA sequencing along with shotgun metagenomics. For this study, we will perform sequencing and metagenomics on the first 16 patients in each arm (32 patients total). The remaining collection will be biobanked for future analysis. These techniques will allow us to measure the abundance of different bacteria, but also evaluate the genetic variation and evolutionary effect from treatment. This will also allow us to evaluate for the differences in the microbiome between responders and non-responders in each treatment arm, considering factors such as UTI, symptoms, pH, etc.

Vaginal Estrogen arm	Baseline	4 months	6 months (if can be completed within the funding period)
Informed consent	X		
Vaginal pH	X	X	Х
Vaginal swab collection	X	X	X (banked)
Urine collection	Х	Х	X (banked)
MESA questionnaire	X	Х	Х
DIVA questionnaire	Х	Х	X

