# **Clinical outcomes**

### **Microbiome analysis**

Whole population DNA will be extracted directly from vaginal and urine samples for both 16S and shotgun-metagenomic sequencing. Sequenced reads will be mapped to the human genome, in order to remove any host DNA contamination. For both 16S and shotgun-metagenomic sequences, reads not aligning to the human genome will then be assigned taxonomic grouping using the Kraken software package. Abundance of taxa/species will be determined by calculating counts per million reads. Changes in microbiome composition will then be determined by comparing the Shannon's diversity index between treatments and sampling timepoints using ANOVA (Yang et al, 2016).

This type of analysis will allow us to further identify the unique microbiome that exists in the urinary bladder. This would not be possible with standard urinary cultures, as without an abundance of 1-2 species, urinary cultures are limited in identifying an existing low count microbiome. This study will add to the microbiome literature in several ways. This type of analysis has not been described using vaginal cultures in patients with rUTI. Furthermore, analysis of change with treatment has not been described in this population as well, from both the urinary and vaginal microbiome perspective. Understanding this information has potential to develop new therapies that may help in treating menopausal women with rUTI.

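### Hypothesis 2 predicts more Lactobacillus and fewer uropathogens, but the only microbiome comparison with a named metric and test (Shannon's index) cannot show that direction, and taxon abundance and vaginal pH have no planned treatment comparison

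*Combined protocol and SAP*

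**What the plan says.** The second hypothesis, at the end of the Background, is directional: "LASER therapy will improve the urinary and vaginal microbiome, decreasing the uropathogenic presence and increasing Lactobacillus". It lists three measurements. The first is "The number of UTI with UPEC isolated from patients". The second is "The pH of the vagina as a proxy for presence of" Lactobacillus. The third is a categorization of vaginal and urinary communities.

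Specific Aim 2 is worded more modestly: "Characterize the urinary and vaginal microbiome at baseline and at 4 months of patients in each group". Sequencing covers the first 16 patients in each arm. The same paragraph mentions looking at microbiome differences between responders and non-responders within each arm, without a metric or a test.

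The Microbiome analysis section says "Abundance of taxa/species will be determined by calculating counts per million reads" and attaches no comparison to those abundances. Change in composition is then to be judged by comparing Shannon's "diversity index between treatments and sampling timepoints using ANOVA".

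Both visit tables schedule vaginal pH at baseline, 4 months and (funding period permitting) 6 months, with extra readings at the LASER treatment visits. The Statistical Analysis section names models for UTI, the MESA and DIVA questionnaires and vaginal histology. It does not mention pH.

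**The concern.** The hypothesis is about which organisms gain and which lose. Shannon's index measures only how evenly reads are spread over taxa. Replacing E. coli by Lactobacillus can lower the index, raise it or leave it where it was, depending on the starting community. A significant Shannon result would not say whether the change was for better or worse, and a null result would not say that nothing changed.

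The data that could speak to the direction will exist: abundances for the sequenced patients, and pH for the whole trial. With no comparison specified, the uropathogen group, the sequencing method (16S or shotgun), the scale and the model would be settled after the data are seen. At stake is the interpretability of the microbiome aim, which the Methods section presents as part of the value of the study and of the case for external funding.

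**Working it through.** **The plan's own figure.** No sample-size or power figure is given for Aim 2. The trial's 94 is for the primary outcome and reproduces at one-sided 5%: n = 2 × 0.16 × 0.84 × (1.645 + 0.842)² / 0.20² = 41.6, so 42 per arm; 42 / 0.9 = 46.7, so 47 per arm, 94 in total. It matters here only because it gives 42 per arm with pH after dropout ("This is accounting for a 10% drop out rate").

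**Shannon's index ignores labels.** H = −Σ p ln p is a sum over shares, so exchanging the names of two taxa leaves it unchanged. This is exact. To illustrate, assume a dominant taxon with share d and k others sharing the rest equally: H = −d ln d − (1 − d) ln[(1 − d)/k].

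- d = 0.79, k = 5: 0.186 + 0.666 = 0.852, whether the dominant taxon is Lactobacillus or E. coli.
- d = 0.30, k = 5: 0.361 + 1.376 = 1.737.
- d = 0.90, k = 5: 0.095 + 0.391 = 0.486.

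The shares 30% and 79% are borrowed from the Lactobacillus colony figures that the Background cites. That they are read shares is my assumption.

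| Move to 79% Lactobacillus from | H, k = 5 | k = 3 | k = 20 |
|---|---|---|---|
| mixed, Lactobacillus 30% | 1.74 to 0.85 (falls) | 1.38 to 0.75 | 2.71 to 1.14 |
| E. coli 79% | 0.85 to 0.85 (no change) | 0.75 to 0.75 | 1.14 to 1.14 |
| E. coli 90% | 0.49 to 0.85 (rises) | 0.43 to 0.75 | 0.63 to 1.14 |

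The same predicted improvement moves H in any direction.

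**What a direct comparison could deliver.** Take a baseline-adjusted arm difference at 4 months, unit variance, baseline correlation ρ, two-sided 5%. The noncentrality is approximately δ/√(1 − ρ²) × √(n/2), where δ is the difference between arms in SD units. The effect sizes and correlations are assumptions; the documents give none. The powers below are simulated, and repeated runs agree to about one percentage point.

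| Outcome | Assumed effects (SD) | Power at ρ = 0.3 / 0.5 / 0.7 |
|---|---|---|
| Taxon abundance, 16 per arm | LASER 1, estrogen 0 | 80 / 87 / 96% |
| | LASER 1, estrogen 0.5 | 29 / 34 / 46% |
| | equal improvement | 5% |
| pH, 42 per arm | LASER 0.5, estrogen 0 | 66 / 74 / 88% |
| | LASER 0.5, estrogen 0.25 | 22 / 25 / 35% |

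Hand check at ρ = 0.5, second row: 0.5/0.866 × √8 = 1.63; the critical t on 29 df is 2.045; Φ(1.63 − 2.045) = 0.34. If 10% dropout leaves 14 per arm (16 × 0.9 = 14.4), the first row becomes 74 / 82 / 94%.

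**Why the within-LASER change stays descriptive.** Patients enter after two or three recent positive cultures, and prior estrogen users have a 1-month washout. Either could produce drift with no LASER effect. An assumed 0.5-SD drift would be significant in a paired test with 16 patients in about 35% (ρ = 0.3) to 67% (ρ = 0.7) of trials.

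**The case against.** Four points on the other side carry weight.

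First, a reader might infer that Shannon's index is the only microbiome comparison in the plan. It is not: Specific Aim 2 also mentions a responder comparison that takes pH into account. That comparison has no metric or test, is made within arms and does not address the treatment effect. The accurate statement is that Shannon's index is the only comparison with a named metric and test.

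Second, a reader might infer that comparing abundances would turn an uninformative analysis into a well-powered one. That requires estrogen to leave the microbiome alone, whereas the Background suggests that estrogen may work by regenerating the vaginal microbiome. With half the LASER effect on estrogen, power roughly halves or worse.

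Third, hypothesis 2 says that LASER improves the microbiome, not that it beats estrogen. The within-LASER change is closest to that wording but is uncontrolled; the arm difference is controlled but answers a somewhat different question. The remedy therefore does not settle the hypothesis either. It does report the quantities that the hypothesis is about.

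Fourth, Aim 2 sets out to characterize, in 32 patients, and Lactobacillus and UPEC are already named, so not every choice is open. This limits the seriousness of the point but does not remove the mismatch.

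A reader might also infer that an unpaired ANOVA is planned for paired samples. The text says only ANOVA; if a repeated-measures form is meant, nothing is lost. The lack of a described tissue collection for histology and of a UPEC-specific analysis are separate points of detail and are not relied on here.

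**Conclusion.** The concern holds in a limited form. Followed exactly, the plan tests a directional hypothesis about named organisms with an index that does not know their names, while the abundances and the pH proxy have no planned treatment comparison. The label-invariance is algebra and needs no assumption; the Shannon profiles and power figures are illustrations under stated assumptions.

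The gain from the remedy is relevance more than power. The arm difference is well powered only if estrogen does little, so intervals matter more than p-values. The pH omission is the more avoidable loss, because pH is scheduled for every patient and not only for the sequenced subset. The documents do not support reading this as a threat to the trial's main conclusion: Aim 2 is exploratory, and the primary non-inferiority analysis does not use these data. The change should be made before the microbiome and pH data are analysed.

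**What to change.** In the Microbiome analysis section:

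- Name Lactobacillus and uropathogen abundance as the main microbiome outcomes for each sample type, labelled exploratory. List the uropathogen taxa, including E. coli.
- Use log counts per million from one named sequencing method, with a stated offset for zeros and a sensitivity check on it.
- Report the arm difference at 4 months adjusted for baseline, and the change from baseline within each arm, all with confidence intervals. Label the within-arm changes descriptive and uncontrolled.
- Keep Shannon's index as a secondary outcome, and state that its analysis accounts for the paired samples.

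In the Statistical Analysis section, add vaginal pH to the mixed-model sentence, using the visits common to both arms (baseline, 4 months, and 6 months if completed).

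The cost is some wording and a little more analysis, with no new samples, visits or assays. The price in inference is limited power, which the text should acknowledge by presenting these results as estimates.

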# **Recurrent UTI**

Our goal is to test the hypothesis that LASER treatment is non-inferior to vaginal estrogen in rUTI patients. If LASER is found to be effective, it would offer clinicians a modality of treatment for these patients that avoids antibiotics and hormone

replacement. It would also offer hope to patients for whom hormones are contraindicated.

# **Strategic Initiatives**

This translational clinical study fulfills multiple strategic initiatives of the Mayo Clinic Enterprise. This novel therapy provides a new service line in regenerative medicine treating women with genitourinary syndrome of menopause with LASER therapy. Expanding the clinical utility based on level 1 evidence that we would provide would fulfill the clinical goals of the Center for Regenerative Medicine. Given that 50% of menopausal women experience symptoms of GSM, this research has potential to impact millions of women in the US and throughout the world.

Incorporating microbiome analysis to this clinical trial opens up further hypotheses of how we can affect an aging microbiome to create a more favorable one within the human body utilizing regenerative technology. This metagenomic data will allow us to better understand this specific population, menopausal women with rUTI, and we may be able to identify avenues to create novel individualized therapies depending on the findings of the microbiome analysis. This fulfills the Center for Individualized Medicine's goals of targeted therapy.
